# Net fluid loss

Current guidelines recommend a target of ~1000ml net fluid loss per day during in-patient diuresis, which generally occurs over a period of up to 9 days (median length of stay for a patient hospitalised with heart failure in the UK). We estimate that a clinically significant difference in daily net fluid loss is 500-1000 ml – a minimum of 4.5L over a 9 day period and 2L over the 4 day period of our study. Such an increase in net fluid loss would indicate a significant increase in diuresis that may shorten hospital admission.

Using the available data on urine output (appendix 7), we expect an average daily fluid loss of 1000ml per day with a standard deviation ranging from 500-1000ml. Patients admitted with heart failure are often breathless on very modest exertion thus we anticipate a drop-out rate of 10% in the control arm. Furthermore, given the lack of reliable clinical data on the tolerability of acetazolamide we have anticipated a higher drop-out rate of 20% in the acetazolamide arm. Thus, to detect a difference of

500-1000ml in net fluid loss per day with statistical power of 80% and two-tailed significance of 5% we would need to recruit a minimum of 35 patients (17 in the control arm and 18 in the acetazolamide arm).

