# Serum chloride concentrations

Low serum chloride is associated with adverse outcome in patients with HF. We estimate a clinically meaningful change in chloride to be -0.9 mmol/L per day over the course of an admission (9 days) and -3.6 mmol/L over the four day period of our study (appendix 7). To detect such a difference with 80% power and 5% two-tailed significant with the above anticipated drop out rate we would need to recruit a minimum of 14 patients in the control arm and 17 patients in the ACZ arm.

We expect two potential confounding factors for the co-primary endpoints: 1) daily salt intake and 2) loss of IV access reducing the amount of IV furosemide given. We will collect data on both potential confounders using a daily dietary sheet (on which the patient will record their meals for the day and from which the daily salt intake will be estimated) and recording the "number of hours of furosemide" per day. We do not expect any patient to have excessive salt intake (defined by the European Society of Cardiology Heart Failure Guidelines 2021 as >5g per day). Any patient with >5g salt intake per day or <20 hours of furosemide per day will be removed from the analysis. Due to the exploratory nature of the study we will conduct an intention to treat analysis and a per-protocol analysis in which only patients who completed the study without deviating from the protocol will be included. Thus, we will recruit a maximum of 50 patients – 23 in the control arm and 27 in the ACZ arm with anticipated drop out of 10% and 20% respectively. The extra patients recruited will also act as a contingency should any patient need to be removed from the analyses for reasons of excess salt intake, prolonged loss of IV access, or for the per-protocol analysis.

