# 10.3 Statistical analysis plan

# Baseline data

# Primary outcomes

Differences in daily net fluid loss and total change in serum chloride (day 1 to day 4) will be compared using independent samples T test. If a difference in number of hours of furosemide per day or salt intake per day is different between the groups then the change in the primary outcomes will be stratified sub groups of hours of furosemide per day and grams of salt per day (cut-offs for group membership will be identified post-hoc).

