# 10.3.2 Primary outcome analysis

# Primary outcomes

We will calculate the median net fluid loss each day and from baseline to day 4 for patients in the ACZ arm and the control arm. We will assess distribution of daily and total fluid loss in both arms, if there is normal distribution we will compare the median net fluid loss using independent samples T-test, if the distribution is not normal we will use the Mann-Witney-U test. A P value <0.05 will indicate a statistically significant difference between the two arms. We will also perform linear regression with total net fluid loss from day 1 to day 4 as the dependent variable and treatment assignment, median daily salt intake and median number of hours of furosemide per day as the independent variables.

We will calculate the median change in serum chloride concentrations between the two groups between baseline and day 4. We will compare the median change in serum chloride concentration using independent samples T test. We will also perform linear regression with total change in serum chloride levels day 1 to day 4 as the dependent variable and treatment assignment, median daily salt intake, and median number of hours of furosemide per day as the independent variables.

The independent samples T test assumes that both net fluid loss (daily and total) and change in serum chloride concentrations between day 1 and day 4 are normally distributed in both groups; this will be tested using distribution curves. It also assumes that there is equal variance in both net fluid loss (daily and total) and change in serum chloride concentrations between day 1 and day 4; this will be tested using Levene's test, the samples will be assumed to have equal variance if Levene's test is P>0.05.

We do not expect any missing data, however any patient with missing data for each of the co-primary endpoints will be excluded from the analysis.

We expect two potential confounding factors for the co-primary endpoints: 1) daily salt intake and 2) loss of IV access reducing the amount of IV furosemide given. Any patient with >5g salt intake per day or <20 hours of furosemide per day will be removed from the analysis.

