# Serum Chloride Change

Data on clinically significant changes in serum chloride levels are lacking. Furthermore, there is conflicting data on the prognostic significance of reductions in serum chloride during in-patient diuresis. However, low serum chloride (<96 mmol/L – hypochloraemia) is strongly and independently associated with adverse outcome in both in- and out-patients with HF. In the PROTECT study patients with hypochloraemia on admission which had corrected by the time of discharge (day

14) were at no greater risk of mortality after discharge than those who had never had hypochloraemia. The median change in chloride between day 1 and day 14 for patients in that group was 5.5 mmol/L (interquartile range (IQR) 4 – 9mmol) which equates to a difference of 0.4 (0.3 - 0.6) mmol/L per day. Conversely, those with normal chloride levels on admission who had developed hypochloraemia by day 14 had a three-fold greater risk of mortality compared to those with normal chloride levels at day 1 and day 14. The median change in chloride between day 1 and 14 for this group was -7 mmol/L (95% CI -10 – 5) equating to -0.5 (-0.7 – 0.4) mmol/L per day.

Data from our local population found similar results: those with hypochloraemia on admission who had normal chloride by the time of discharge were at no greater risk of mortality compared to those who had normal chloride levels on admission and discharge. The median change in chloride levels in this group was 6 (5 – 8) mmol/L over a median in-patient stay of 12 days; 0.5 (0.4 – 0.7) mmol/L per day. Conversely, those with normal chloride levels on admission who had hypochloraemia at discharge were at 50% increased risk of adverse outcome. The median change in chloride levels in this group was -8 (-12 – -5) mmol/L over a median in-patient stay of 13 days; -0.6 (-0.9 – -0.4) mmol/L per day. The median chloride on admission in patients with normal chloride levels on admission was 100 (98 – 103) with a standard deviation of 3 mmol/L thus a 8 mmol/L reduction in serum chloride concentrations would cause hypochloraemia in the majority of patients; similar to the median change in chloride levels on admission who develop hypochloraemia by discharge (table 2).

Table 2 – Available Data on Changes in Serum Chloride Levels During In-patient Diuresis

Study		Ter Maarten et al	[name] et al
		(2016)	(2022)

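### Baseline chloride enters no primary analysis, while the additional primary regressions and a conditional stratification use salt intake and furosemide hours, which are measured after randomisation

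*Protocol*

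**What the plan says.** Section 10.3.2 sets the lead comparison for each co-primary. Net fluid loss is compared by t-test, or by Mann-Whitney if the distribution is not normal. For chloride: "We will compare the median change in serum chloride concentration using independent samples T test". Despite the word median, this is an unadjusted comparison of mean change scores.

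The same section then adds a linear regression for each co-primary. For net fluid loss the four-day total enters "as the dependent variable and treatment assignment, median daily salt intake and median number of hours of furosemide per day as the independent variables"; the chloride regression uses change in chloride with the same three predictors. Baseline chloride is among the baseline data in section 7.6 and in the baseline table of section 10.3.1, but it is a covariate in neither regression.

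Section 10.3 adds a conditional step. If the arms differ in furosemide hours or salt intake, the primary outcomes are to be stratified by those variables, and "cut-offs for group membership will be identified post-hoc". Sections 10.1 and 10.3.2 describe both variables as potential confounders. Both are recorded daily during the four treatment days.

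**The concern.** There are two separate issues.

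**Precision for chloride.** A change score carries the measurement noise and regression to the mean of the baseline value. Where the baseline is available in everyone, adjusting for it costs nothing to collect and normally narrows the interval. Section 2 says the results are meant to inform a larger trial, so the precision of the chloride effect is part of what the pilot delivers.

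**Covariates measured after randomisation.** A variable recorded after allocation cannot confound a randomised comparison. It is either noise or partly a consequence of treatment. The protocol supplies possible routes from treatment to both variables:

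- Furosemide hours: under section 8.5 the infusion lasts only while there is a clinical need for it. Section 7.8 (Visits 3 to 5) provides for de-escalation, and the trial is open label (section 7.4).
- Salt intake: section 2.2 lists nausea, taste disturbance and reduced appetite among the common effects of acetazolamide, and any of these could change what is eaten.

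If either route operates, the adjusted coefficient is no longer the total effect of assignment. The stratification is triggered by a difference between arms, which is when such a route is most plausible. Cut-offs chosen after seeing the data add a further data-driven choice in about 40 patients.

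**Working it through.** **Inputs.** Section 10.1 gives the chloride target, "3.6 mmol/L over the four day period of our study", and the error rates: "To detect such a difference with 80% power and 5% two-tailed significant with the above anticipated drop out rate". On dropout it says "we anticipate a drop-out rate of 10% in the control arm" and expects a "higher drop-out rate of 20% in the acetazolamide arm". Appendix 2 gives admission chloride "with a standard deviation of 3 mmol/L". That is an SD of a level; no SD of change and no correlation r are given. Assumptions: equal SDs at day 1 and day 4, and r from 0.3 to 0.9.

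**The plan's own figure.** With difference 3.6, SD 3, two-sided 5% and 80% power, the t-based solution is 11.94, so 12 per arm.

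- Control: 12/0.9 = 13.3, so 14 (stated: 14).
- Acetazolamide: 12/0.8 = 15 (stated: 17).
- Total: 29 against the stated 31.

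The figure reproduces to within two patients if 3 mmol/L is used as the SD of change.

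**Gain from baseline chloride.** With common SD s:

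- variance of change = 2s²(1−r)
- residual variance of ANCOVA = s²(1−r²)
- ratio = (1+r)/2

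The power column takes the SD of change as 3 and 11 evaluable per arm (normal approximation, where the unadjusted test has 80%). The ANCOVA residual SD is then 3·√((1+r)/2).

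| r | variance ratio | saving | residual SD | power |
|---|---|---|---|---|
| 0.3 | 0.65 | 35% | 2.42 | 94% |
| 0.5 | 0.75 | 25% | 2.60 | 90% |
| 0.7 | 0.85 | 15% | 2.77 | 86% |
| 0.9 | 0.95 | 5% | 2.92 | 82% |

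These are large-sample ratios. Estimating the slope multiplies the ANCOVA variance by about 1 + 1/(N−4). At N = 40 this is 1 + 1/36 = 1.028, so at r = 0.9 the net ratio is 0.95 × 1.028 = 0.98. At N = 22 it is 1 + 1/18 = 1.056, and 0.95 × 1.056 = 1.00, so the gain is gone. At r = 0.5 and N = 40 the ratio is 0.75 × 1.028 = 0.77.

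**Chance imbalance.** With 20 per arm and SD 3, the standard error of the baseline difference is 3·√(2/20) = 0.95 mmol/L. A one-standard-error imbalance shifts the expected change-score difference by (1−r) × 0.95. At r = 0.5 this is 0.47 mmol/L, or 0.47/3.6 = 13% of the target.

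**Adjusting for a post-randomisation exposure.** This is an illustrative simulation with 400,000 patients per scenario. All its values are assumed: direct effect 1000 mL, 100 mL per furosemide hour, hours centred on 22 in the control arm. The unmeasured factor, where present, adds 1 hour and 300 mL per SD.

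| treatment effect on hours | unmeasured common cause | unadjusted (total effect) | adjusted for hours |
|---|---|---|---|
| none | no | 998 | 998 |
| −1 hour | no | 894 | 993 |
| −1 hour | yes | 902 | 1152 |
| +1 hour | no | 1100 | 999 |
| +1 hour | yes | 1095 | 847 |

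If hours do not respond to treatment, adjustment does no harm. If they do, the adjusted figure departs from the total effect, upwards or downwards. The table shows direction only and is not an estimate of bias in this trial.

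**The case against.** The strongest reply is that the lead comparisons are unadjusted and the regressions are expressly additional. That stands. A reader might infer that the primary result itself is conditioned on salt and furosemide hours, so that part of the treatment effect is adjusted away. The text does not support this: the t-test and Mann-Whitney contrasts carry no covariates, and where the added models do go wrong the direction is not fixed.

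Second, the furosemide route is narrowed by other rules. The stated worry is loss of IV access. Patients whose diuretic is de-escalated are treated as having completed early (section 7.8), and those under 20 hours per day are removed (sections 10.1 and 10.3.2). Most patients left would have 20 to 24 hours, summarised as a median. This limits the size of any distortion but does not remove it. It also says nothing about salt below the 5 g limit. The removal rule is itself selection on a post-randomisation variable and is a separate matter.

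Third, omitting the baseline is inefficient, not invalid. The change-score t-test is unbiased under randomisation, and its standard error already reflects chance imbalance. Chloride also has headroom, needing 31 patients against 40 to 50 planned. All of this stands, and it keeps the point modest.

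Finally, a pilot may explore. It may, but exploratory models should be labelled so, and the stratification sits under the primary outcomes without that label.

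**Conclusion.** The point holds in limited form. No planned primary analysis uses baseline chloride. Adding it would save between 35% and 5% of the error variance for r from 0.3 to 0.9, slightly less at this sample size and close to nothing at r = 0.9. This rests on equal SDs at the two times and on a correlation the protocol does not give, and it concerns chloride only. The documents give no figure from which to claim a precision gain for net fluid loss.

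The additional regressions and the conditional stratification rest on variables that may respond to treatment. They may be biased for the total effect in either direction, and calling the variables confounders is wrong in a randomised comparison. That bias is a possibility, not an established fact: it requires acetazolamide to change salt intake or furosemide hours. The unadjusted lead comparisons are not affected by this adjustment.

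**What to change.** In Protocol section 10.3:

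- Make the primary chloride analysis an ANCOVA of day-4 chloride (or change) on treatment and baseline chloride, reporting the adjusted mean difference with a 95% confidence interval.
- Keep the unadjusted comparison as primary for net fluid loss.
- Delete the stratification by furosemide hours and salt intake with cut-offs chosen after the data are seen.
- Report salt intake and furosemide hours descriptively by arm. If a regression on them is kept, label it exploratory, do not use it to estimate the treatment effect, and drop the description of these variables as confounders.

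The cost is a wording change to the protocol, made through its amendment route. Baseline chloride is already collected, so no new data are needed.

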# 8.1 Missed Doses

If dose is missed, the missed dose should be taken as soon as remembered. However, if this is within two hours of the next dose then skip the missed tablet and carry on taking the rest of the tablets as usual. Do not take a double dose to make up for a forgotten dose. Following this patients can then resume their regular dosing schedule. If intravenous access is lost at any time during the study period the patient will not have been receiving the active comparator (IV furosemide). We will record the amount of time without IV furosemide in the CRF and if a patient has >6 hours without receiving IV furosemide we will attempt to replace the patient data.

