# 9.2 Operational definitions for (S)AEs

Due to the pilot and exploratory nature of this study **all** adverse events and adverse reactions will be recorded. All serious adverse events serious adverse reactions, and suspected unexpected serious adverse reactions will be reported.. This will enable collection on safety data for the use of ACZ concurrently with high dose loop diuretics as well as data on the tolerability of treatment for a future trial.

	Asymptomatic hypotension (systolic blood pressure (SBP) <90 mmHg)
	Symptomatic hypotension (SBP <90 mmHg and symptoms of: dizziness or presyncope)
	Asymptomatic hyponatraemia (serum sodium concentrations <130 mmol/L)
Adverse Events	Symptomatic hyponatraemia (serum sodium concentrations <130 mmol/L and symptoms of fatigue, nausea, vomiting, or headache not promoting further treatment or investigation)†
	Flare of gout requiring oral treatment and analgesia
	Decrease in estimated glomerular filtration rate >50% of baseline value
	† Treatment of headache with analgesia not included in this definition however treatment of nausea or vomiting with antiemetic is.
	Symptomatic hypotension with sequelae (SBP <90 mmHg and symptoms of: dizziness or presyncope and fall or injury as a direct result)
	Symptomatic hyponatraemia with sequelae (serum sodium concentrations <130 mmol/L and symptoms of fatigue, nausea, vomiting, headache which prompt further treatment or investigation,† or confusion or seizure deemed secondary to hyponatraemia).
	Decrease in eGFR >100% of baseline value or serum creatinine >221µmol/L
	Deterioration in condition during trial defined as:
Serious Adverse Events	
 
Deemed to need escalating doses of loop diuretic or the addition of a second diuretic agent such as thiazide diuretic.
 
Deemed to need inotropic support
 
New diagnosis of infection
 
New diagnosis of another concurrent illness that will prolong hospital stay
 
Transition to end-of-life care
 
Death
 

	Overdose of ACZ or furosemide infusion defined as 1) >500mg given per day of ACZ or 2) >240mg IV furosemide per day.
Adverse Reactions	Metabolic acidosis bicarbonate <23 mmol/L
	Hyperchloraemia 107-110 mmol/L

	Teaching Hospi	tals
	Any of the following possible side effects of acetazolamide that are NHS tolerable to the patient: haemorrhage, ataxia, depression, diarrhoea,	Trust

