# 9.9 Overdose

Any overdose of ACZ or furosemide will be reported as an SAE and recorded in the medical notes, CRF and deviation log as soon as the study doctor is alerted. The sponsor will be alerted within 24 hours of a suspected serious breach. Overdoses will be observed from the electronic prescribing record. A patient receiving an overdose will be removed from analysis and replaced. The incident will also be reported using the Hull University Teaching Hospital Trust incident reporting system – Datix.

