# 10.6 Subject population

As this is a pilot and exploratory study, we will perform both an intention to treat analysis on all patients completing the study so that we can most accurate describe the clinical effects of ACZ including tolerability and side effects and a per-protocol analysis so we can most accurately assess the primary endpoints.

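### No planned analysis compares all randomised patients as allocated: patients are removed for post-randomisation events, and the intention-to-treat set is limited to completers

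*Protocol*

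**What the plan says.** The removal rule for salt intake and furosemide hours stands in the protocol's primary analysis (Section 10.3.2) and again in Section 10.1 under serum chloride: "Any patient with >5g salt intake per day or <20 hours of furosemide per day will be removed from the analysis". Section 10.1 then justifies extra recruitment by patients who may be "removed from the analyses for reasons of excess salt intake, prolonged loss of IV access, or for the per-protocol analysis". Salt and IV access are named there as reasons in their own right, beside the per-protocol restriction.

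Section 10.6 gives the only definition of the other set: "we will perform both an intention to treat analysis on all patients completing the study". It expects this set to describe tolerability, and the per-protocol set to give the more accurate reading of the primary endpoints.

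Other sections take out further patients:
- Section 10.3.2: "any patient with missing data for each of the co-primary endpoints will be excluded from the analysis". Section 10.7 tries to replace anyone lacking data on either primary endpoint and rules out imputation.
- Section 9.9: "A patient receiving an overdose will be removed from analysis and replaced". Section 9.2 includes ">240mg IV furosemide per day" in the definition of overdose.
- Section 8.1: "if a patient has >6 hours without receiving IV furosemide we will attempt to replace the patient data".
- Section 7.8 stops study investigations once a patient's diuretic treatment is de-escalated at day 3 or day 4.

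Section 4 says the trial is powered for superiority on both primary endpoints. Section 10.1 anticipates drop-out of 10% on control and 20% on acetazolamide.

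**The concern.** Randomisation makes the arms comparable only for the full set of patients it allocated. Salt intake, hours of infusion, completion of four days and availability of day 4 data all become known afterwards, staff and patients know the allocation, and each can depend on treatment. A patient who decongests quickly may be de-escalated, fall below 20 hours of furosemide and have no day 4 values. A patient who does not tolerate acetazolamide may stop. Under Section 7.9, certain events lead to withdrawal only in the acetazolamide arm. One of them is severe hyperchloraemia, and serum chloride is a co-primary endpoint.

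At stake are both co-primary estimates. Section 2 intends them to inform the design of a large multi-centre trial. The completer set also cannot serve the tolerability purpose Section 10.6 gives it, because patients who stop for intolerance are not in it.

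**Working it through.** **1. The plan's own figure.** Section 10.1 gives 35 patients (17 + 18) for net fluid loss at 80% power and two-sided 5%. The per-arm formula is n = 2[(1.960 + 0.842) × SD/δ]².
- With δ/SD = 1 (500/500 or 1000/1000), n = 2 × 2.802² = 15.7.
- Inflating by (1 + d): 15.7 × 1.1 = 17.3 and 15.7 × 1.2 = 18.8, about 36 in all.
- Inflating by 1/(1 − d): 17.4 and 19.6, about 37 in all.

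The stated 35 is reproduced to within two patients, but only at δ/SD = 1. Inflating for drop-out treats drop-outs as contributing nothing to the analysis, which agrees with Section 10.6.

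**2. Who is left.** With the protocol's maximum of 50 (23 control, 27 acetazolamide) and its drop-out rates:
- control 23 × 0.9 = 20.7; acetazolamide 27 × 0.8 = 21.6; total 42.3, or 85% of those randomised.
- At 40 patients, assuming 20 per arm: 18 + 16 = 34, again 85%.

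Salt and furosemide-hours removals come on top, and the protocol gives no frequency for them. If they take 5% to 30% of completers (an assumption), the analysed share of 50 falls to between 80% and 59%.

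**3. Illustrative size.** If the lowest fraction p of a normal outcome is lost, the mean of the rest rises by φ(z)/(1 − p) SD, where z is the p-quantile.
- Acetazolamide, p = 0.20: φ(0.8416)/0.8 = 0.350 SD.
- Control, p = 0.10: φ(1.2816)/0.9 = 0.195 SD.
- Net shift towards acetazolamide: 0.350 − 0.195 = 0.155 SD.

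| SD (mL/day) | Source | Net shift (mL/day) |
|---|---|---|
| 500 | Section 10.1, low end | 78 |
| 1000 | Section 10.1, high end | 155 |
| 1160 | Appendix 2, high-dose arm of the cited diuretic-dose trial | 180 |

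The lower end of the target difference is 500 mL/day. If the best responders left at the same rates, the shift would be the same size with the opposite sign. No mmol/L figure is given for chloride, because the documents state an SD for admission chloride (3 mmol/L) but none for the four-day change.

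**4. Weaker selection.** Step 3 assumes loss is wholly determined by outcome. A simulation with no true effect, SD 1000 mL/day, 23 and 27 patients, and 10% and 20% drop-out leaning towards poorer responders gave these biases:

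| Correlation of drop-out with outcome | Bias (mL/day) |
|---|---|
| 0 | about 0 |
| 0.3 | 53 |
| 0.5 | 74 |
| 0.8 | 123 |

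At 0.8 the type I error was about 7.5% against a nominal 5%.

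**5. What keeping everyone is worth.** At δ/SD = 1, power is 0.90 with 42.3 completers and 0.94 with all 50, provided outcomes are obtained for everyone kept.

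**The case against.** Section 4 states that the primary aim is feasibility and tolerability, and Section 13.10 says the study is not designed to detect a treatment benefit. That tempers the matter. It does not remove it, since Section 4 also claims superiority powering and Section 10.3.2 tests at P<0.05.

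The completer label needs a qualifier. Section 7.8 deems patients de-escalated early to have completed, and at days 2 and 3 says their data are kept, so some with fewer than four days of treatment may enter the intention-to-treat set. The missing-data and 20-hour rules could still remove them.

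Four stronger readings are tempting, and the documents do not support them:
- *A bias of −226 to +406 mL/day.* These are 0.195 × 1160 and 0.350 × 1160. Each needs one arm to lose only its worst patients while the other loses none selectively, at an SD above the planning range.
- *That nothing planned would reveal the problem.* Cause-specific drop-out is a secondary endpoint (Section 3.5), compared between arms in Section 10.3.3, and Section 10.3.1 plans a CONSORT diagram. Unequal loss would be seen; an unbiased estimate would still be missing.
- *That the overdose rule is shown to discard treatment failures.* Section 9.2 lists escalation of loop diuretic and overdose as separate entries, and Section 9.9 handles overdose as an incident. The literal definition could catch deliberate escalation, but that is an ambiguity.
- *That the furosemide-gap rules flatly contradict each other.* Section 8.1 triggers an attempt at replacement and is not expressed per day; Sections 10.1 and 10.3.2 trigger removal and are per day. They are unaligned.

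**Conclusion.** The point holds. As written, every stated analysis set is selected on events after randomisation, and no set consists of all randomised patients as allocated. An SAP that followed these rules would inherit the defect. This rests on two readings of the text: that the salt and furosemide-hours removals are not confined to the per-protocol set, as the list in Section 10.1 indicates, and that Section 10.6 supplies the operative definition of intention to treat.

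The size and direction of bias cannot be known from the document. The net 0.155 SD (78 to 155 mL/day at the planned SD) is an illustration. It assumes normal outcomes, the protocol's own drop-out rates, and loss of the poorest responders in both arms. It would be smaller with weaker selection and reversed if early responders are the ones lost. Even so, against a 500 mL/day target it is large enough to matter.

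**What to change.** 1. Define the primary set as all randomised patients, analysed as allocated, using every available daily fluid value and chloride value. A repeated-measures mixed model would do this without imputation, with its missing-at-random assumption stated.
2. Apply the salt, furosemide-hours, overdose and completion exclusions only in a labelled per-protocol sensitivity analysis, and drop the statement that this set assesses the primary endpoints most accurately.
3. Allow extra patients to be randomised, but never to displace the data of those already randomised.
4. Where consent allows, keep recording fluid balance and the routine serum chloride to day 4 after early stopping or de-escalation. Without this, changing the analysis set cannot recover outcomes that were never collected.
5. Reconcile Section 8.1 with Sections 10.1 and 10.3.2 on the furosemide gap, and the entries on overdose and on escalation of loop diuretic in Sections 9.2 and 9.9.

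The cost is revised wording, a small change to the visit schedule, and some dilution of the estimate by non-adherence. Values after withdrawal of consent will still be missing, so the model's assumption remains an assumption.
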